5.3.3 Analysis of Primary Endpoint

PRIMARY ENDPOINT, PHASE 2 PART:

Grade ≥3-Infection-free survival in the treatment arm compared to the observation arm 24 weeks after treatment/observation is initiated. The proportion of patients with the primary endpoint will be assessed at 24 weeks after enrollment using a chi-squared test of proportions. - This is a non-

inferiority analysis as detailed in statistical analysis plan to assure safety of the combination treatment in this preemptive trial population.

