Study Centers:	Subjects will be enrolled in approximately 7 centers in Denmark, Sweden and the Netherlands.	
Study Objectives:	The aim of the study is to evaluate whether short-term, pre- emptive combination treatment with venetoclax plus acalabrutinib in patients with high risk of infection and/or CLL treatment can change the natural history of immune dysfunction in CLL in terms of the long-term risk of serious infections and diminish the need for cytotoxic chemotherapy. (Without an increased risk of infection during treatment in that group)	
	Primary Objective phase 2 part:	
	 Grade ≥3-Infection-free survival in the treatment arm compared to the observation arm 12 weeks after finishing treatment, (24 weeks after treatment initiation). This is a non-inferiority analysis as detailed in the statistical analysis plan to assure safety of the combination treatment in this preemptive trial population. 	
	Primary Objective optional phase 3 part:	
	 Grade ≥3-infection free and CLL-treatment-free survival 2 years after enrollment 	

Secondary Objective(s):

- Grade ≥3-infection free and CLL-treatment-free survival at end of treatment, 1 year and 2 years after enrollment
- Rate of overall survival (OS) and cause of death
- Treatment free survival
- Rate and CTCAE V5.0 grade of infections
- Response rate and duration according to IWCLL criteria
- Treatment related adverse events, type, frequency and severity during and for 2 years after treatment
- Immune function as assessed by immune phenotyping, functional TruCulture assays and measurements of cytokine levels

Exploratory Objective(s):

- MRD levels in bone marrow and peripheral blood
- Quality of life during and for 2 years after treatment, QLQC30 and CLL17

Study Design:

Newly diagnosed patients with CLL will be assessed by the CLL-TIM algorithm for high risk of infection and/or early CLL treatment need during the screening period. Only patients identified as at high risk, who do not currently fulfil IWCLL treatment criteria, will enter the trial. Assessment of variables for the risk profile including the baseline characteristics and laboratory result based Machine Learning algorithm CLL-TIM will be performed centrally through a plug & play model, which will be part of the eCRF system.

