3.9 DURATION OF THERAPY

Duration of treatment with acalabrutinib and venetoclax is for 3 cycles of 28 days; the end of trial is defined as seven years after start of treatment or observation with close follow up for the first two years, while follow up for AESI's, CLL treatment and survival continues until end of trial. The primary endpoint for the phase 2 part is 6 months after start of treatment or observation.

3.10 DOSING DELAYS AND MODIFICATIONSIn the case of AEs attributed to both acalabrutinib and venetoclax, the local investigator should decide whether dose

modifications apply to one or both drugs in collaboration with the sponsor, as no data on pharmacokinetic interaction between acalabrutinib and venetoclax are currently available.

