5.2 MISSING DATA HANDLING

No imputation of values for missing data will be performed except that missing or partial start and end dates for AEs and concomitant medication will be imputed according to prespecified, conservative imputation rules. Subjects lost to follow-up (or drop out) will be included in statistical analyses to the point of their last evaluation.

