5.3 ENDPOINT DATA ANALYSIS

5.3.1 Safety Endpoint(s) for the Phase 2 Part as Primary Endpoint

- Grade ≥3-Infection-free survival 24 weeks after treatment initiation. This is a non-inferiority analysis as detailed in statistical analysis plan to assure safety of the combination treatment in this preemptive trial population.
- Rate and CTCAE grade of infections
- Treatment related adverse events, type, frequency and severity during and for 2 years after treatment

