5.3.4 Secondary Efficacy Endpoint

CLL-treatment-free survival (TFS), is defined as the time from first dose or start of observation to initiation of (another) CLL-treatment or death from any cause.

OS is defined as the time from first dose or start of observation to death from any cause. Data for subjects who are still alive at the time of data cutoff date, lost to follow-up, have discontinued the study (or, if no post-baseline assessment, at the time of first dose plus 1 day). Duration of OS will be estimated using Kaplan-Meier methodology. Approximate 95% CIs for median duration of OS will be computed using the formula proposed by Brookmeyer and Crowley.

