6.1.1 Adverse Event Reporting Period

The AE reporting period for this study begins when the subject receives the first dose of study drug or Cycle 1 Day 1 for the observation arm of the study and ends with the SFU visit.

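### The primary endpoint is defined from start of treatment or observation but tested from enrollment, and the drop-out rule cannot be carried out in a fixed-time chi-squared proportion

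*Protocol*

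**What the plan says.** **Time point.** Section 5.3.3 first places the endpoint "24 weeks after treatment/observation is initiated" and then states the test: "The proportion of patients with the primary endpoint will be assessed at 24 weeks after enrollment using a chi-squared test of proportions". Section 5.3.1 gives "Infection-free survival 24 weeks after treatment initiation". Section 3.9 says "The primary endpoint for the phase 2 part is 6 months after start of treatment or observation". The Synopsis and section 2.1 place it 12 weeks after the end of treatment and equate that with 24 weeks from initiation. Appendix 1 schedules a visit 24 weeks after C1D1.

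**Gap before start.** Section 3.6.4 allows up to 14 days between randomization and the start of treatment or observation.

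**Event recording.** Under section 6.1.1 the adverse event reporting period "begins when the subject receives the first dose of study drug or Cycle 1 Day 1 for the observation arm". Appendix 1, however, ticks adverse events at prescreening and screening.

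**Drop-outs.** Section 5.2 rules out imputation except for certain dates and adds: "Subjects lost to follow-up (or drop out) will be included in statistical analyses to the point of their last evaluation".

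**Time-to-event endpoints.** In section 5.3.4, treatment-free survival (TFS) "is defined as the time from first dose or start of observation to initiation of (another) CLL-treatment or death from any cause". Overall survival (OS) has the same origin and is the only endpoint for which Kaplan-Meier estimation is named.

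**The concern.** Two consecutive sentences of section 5.3.3 give the primary endpoint two time zeros, so the same patient can be an event under one and not under the other. If the enrollment clock is used and recording begins at C1D1, the opening days of the window go unobserved.

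Separately, the rule in section 5.2 is a censoring rule, which suits a time-to-event estimate. The prescribed primary analysis compares proportions at a fixed time and has no place for partial follow-up.

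Unrecorded days, and drop-outs counted as infection-free, both lower the measured risk. In a non-inferiority comparison meant to show safety, that leans toward a favorable result. Section 5.4 makes non-inferiority a condition for expansion to phase 3, and with 25 patients per arm the verdict turns on very few events.

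**Working it through.** **Inputs from the protocol** (Synopsis, section 6, section 3.6.4): 25 per arm; 10% risk in both arms within 6 months; 80% power; margin 21 points; start within 14 days of randomization.

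**Assumptions, not in the protocol:** one-sided alpha 0.05; constant hazard; drop-out of 4%, 10% or 20%, uniform over 24 weeks; enrollment date taken as the randomization date.

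**1. The plan's own margin.** (z0.95 + z0.80) × √(2 × 0.10 × 0.90 / 25) = (1.645 + 0.842) × 0.0849 = 0.211. This reproduces the 21%. One-sided 0.025 would give 0.238, so 0.05 is the level that fits.

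**2. Clock.** With the full 14-day gap and no earlier recording, 168 − 14 = 154 days are observed.
- A true 10% reads 1 − 0.90^(154/168) = 9.2%. The loss is 0.8 points, or 25 × 0.008 = 0.2 events per arm.
- A true 31% reads 1 − 0.69^(154/168) = 28.8%.
- A patient starting on day 14 has 24 − 2 − 12 = 10 weeks after a full 12-week course, not the stated 12.
- If 6 months means 182.5 days, 10% at 6 months is 1 − 0.90^(168/182.5) = 9.2% at 24 weeks.

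**3. Drop-outs counted event-free.** If a fraction d leaves uniformly over the window, the apparent risk is (1 − d)p + d[1 − (1 − e^(−L))/L], with L = −ln(1 − p).
- p = 0.31: L = 0.371 and the bracket is 0.165. For d = 0.10, 0.279 + 0.0165 = 29.5%. For d = 0.20, 0.248 + 0.033 = 28.1%.
- p = 0.10: L = 0.105 and the bracket is 0.051. For d = 0.10, 9.5%. For d = 0.20, 9.0%.

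**4. False non-inferiority at the margin (true 31% v 10%).** Exact binomial enumeration, 25 per arm, one-sided 0.05:

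| Scenario | Treatment reads | Control reads | Score test | Wald rule |
|---|---|---|---|---|
| Full follow-up | 31.0% | 10.0% | 4.7% | 6.2% |
| 10% drop-out, both arms | 29.5% | 9.5% | 5.6% | 7.6% |
| 20% drop-out, both arms | 28.1% | 9.0% | 6.5% | 9.1% |
| 4% drop-out, treatment only | 30.4% | 10.0% | 5.2% | 6.9% |
| 10% drop-out, treatment only | 29.5% | 10.0% | 6.1% | 8.1% |
| 20% drop-out, treatment only | 28.1% | 10.0% | 7.8% | 10.4% |
| 14 days unrecorded, both arms | 28.8% | 9.2% | 5.9% | 8.2% |

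With 2 control infections, 3 treatment infections pass and 4 fail under either test.

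**5. Drop-outs excluded instead.** Power is Φ(0.21 / √(0.18 / (25(1 − d))) − 1.645). It falls from 79.7% to 78.2%, 75.9% or 71.5% at 4%, 10% or 20% drop-out.

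**The case against.** Four points count against a stronger reading, and each stands at least in part.

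**The clock.** A reader might infer several rival clocks. In fact the Synopsis, sections 2.1, 3.9 and 5.3.1, the first sentence of 5.3.3 and the Appendix 1 visit all rest on the start of treatment or observation. The outlier is the enrollment wording in 5.3.3. The 6 months in 3.9 shares that time zero, and since the protocol calls three 28-day cycles 3 months, it may mean 168 days. The contradiction remains because the outlier sits in the sentence that specifies the test.

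**Recording.** A reader might infer that infections before C1D1 certainly go unrecorded. Appendix 1 ticks adverse events at screening. If that governs, the gap closes, and on a C1D1 clock there is none. What the text shows is a conflict between 6.1.1 and Appendix 1.

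**Toxicity.** A reader might infer that patients stopping for toxicity would count as infection-free. Section 3.13 keeps those who discontinue therapy under follow-up for safety and survival, and section 4.3 continues adverse event follow-up to 2 years. Section 3.14 reserves removal for events such as withdrawn consent, loss to follow-up or death. Only patients who truly leave are affected.

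**The SAP.** The non-inferiority analysis is deferred to the SAP, where analysis sets and sensitivity analyses normally belong. So the protocol's silence on patients who never start is not itself a fault, and nothing says they are excluded. But the protocol fixes the test, the time point and the drop-out rule itself, and an SAP cannot follow all three as written.

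That one event can flip the verdict is true of any threshold at 25 per arm. It shows sensitivity, not bias.

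**Conclusion.** The point holds as an internal conflict that should be corrected before analysis. Section 5.3.3 gives two time zeros, and the section 5.2 rule does not fit the test in 5.3.3. Where the conflict changes the measured risk, it lowers it and favors non-inferiority.

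The size is modest. The clock loss of 0.8 points is a worst case: every patient starts on day 14 and nothing is recorded earlier. The drop-out figures rest on assumed rates, constant hazard, an inferred alpha and the choice of test. The upper range of 6.1-7.8% further requires that drop-out occur in the treatment arm alone; with equal drop-out it is 5.6-6.5%. The protocol gives no drop-out rate, and at 4% in the treatment arm only the figure is 5.2% against 4.7%. The documents do not support a claim of serious mis-measurement or of a systematic loss of toxicity cases.

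**What to change.** 1. Replace enrollment in 5.3.3 and 6 months in 3.9 with day 168 from one time zero for both arms, most simply C1D1 or start of observation, which matches the Appendix 1 visit. Moving the whole endpoint to randomization would bring back the 10-week problem and depart from that visit.
2. Analyze all randomized patients as assigned. State an origin for those who never start, for example the randomization date, and apply it to TFS and OS too. Say how an event between randomization and C1D1 counts.
3. Reconcile 6.1.1 with Appendix 1 so that grade ≥3 infections and deaths are recorded from randomization.
4. Estimate each arm's 24-week risk by Kaplan-Meier, censoring drop-outs at last evaluation as 5.2 intends, and compare the upper confidence bound of the difference with 21 points.
5. Add a sensitivity analysis counting treatment-arm drop-outs as events, because censoring alone does not correct informative drop-out.

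**Cost:** wording changes, a little extra analysis and up to 14 more days of event recording per patient. No new visits are needed.

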5.3.4 Secondary Efficacy Endpoint

CLL-treatment-free survival (TFS), is defined as the time from first dose or start of observation to initiation of (another) CLL-treatment or death from any cause.

OS is defined as the time from first dose or start of observation to death from any cause. Data for subjects who are still alive at the time of data cutoff date, lost to follow-up, have discontinued the study (or, if no post-baseline assessment, at the time of first dose plus 1 day). Duration of OS will be estimated using Kaplan-Meier methodology. Approximate 95% CIs for median duration of OS will be computed using the formula proposed by Brookmeyer and Crowley.

5.3.5 Biomarker Analyses including Immune Function and MRD

The diagnostic immunological profiling tool is based on novel, standardized techniques revealing in-depth information on immune phenotype and -function, allowing for standardized and robust data readout and ensuing technology transfer. These assessments are based on a collaboration with [name], PhD, Rigshospitalet and the Persimune.org project.

These investigations will be performed at a few central laboratories to assure quality and interlaboratory reproducibility. In combination with MRD results and assessment of subclonal development, immune phenotyping data may indicate optimal treatment length (6 months or 3 months).

- Immune phenotyping: A 10-color flow cytometry whole blood panel comprising 10 different tests has been custom-designed (DuraClone, Beckman Coulter) and is currently under validation at the Dept. of Clinical Immunology, Rigshospitalet. The ten different flow tests (I-X) evaluates: I) Major cell lineages in the blood (proportions and counts), II) B cell subsets, III) T cell subsets, IV) T cell receptor (TCR) subsets, V) Regulatory (Treg) and Th17 cells, VI)

 Dendritic cells, VII) Myeloid cells, VIII) Erythrocytes as surrogates for asplenism, IX) Platelets and platelet-leukocyte co-aggregates and X) Neutrophil phagocyte function. The panel captures multiple patterns predictive for cancer patients i.e. deviated maturation, acute/chronic activation, exhaustion, migration/trafficking and expression of immune checkpoint markers (PD-1, PD-1L, CTLA-4, FoxP3, Helios, CD25, TLR2, TLR4, CD38) which will also be extended with assessment of NK cell function and subtypes as well as additional immune activation markers.¹⁻⁸
- **Immune function**: Stimulated immune response & platelet function are assessed by TruCulture® (Myriad RBM), which assesses the induced innate and adaptive immune

responses to whole blood ligand stimulation. Five different stimuli I-V are applied to screen the response to signaling pathways via Toll Like Receptors (TLRs), critical for the anticancer immune response as TLR ligands may break tolerance to self-antigens and promote immune responses to tumor antigens^{9,10}: I) Zymosan; II) Poly I:C; III) Resiquimod; IV) ODN + LPS and V) NegCo. TruCulture® are currently validated at the Dept. of Clinical Immunology, Rigshospitalet and being tested for assessment of immune function in CLL at baseline and during treatment with targeted small molecules. TruCulture® provides an extensive data-readout, with cytokine response data available within days whereas Multiplate®/TEG® provides real-time results also on platelet function and complement cascades. Furthermore, transcriptomics by RNAseq assures in depth analyses of the molecular basis for immune changes upon treatment in stimulated and unstimulated cells.

In addition to the direct assessment of immune dysfunction by this approach at baseline, during and after treatment, infections will be closely monitored during the whole study as a readout for immune dysfunction. Furthermore, microbiomic assessment of the microbiological diversity and changes upon preemptive treatment will be assessed by 16S and shotgun sequencing of skin swaps, saliva and feces samples at baseline and during treatment for an in-depth assessment of immune dysfunction and impact on the microbiome in parallel to microenvironmental changes. By applying the extensive translational program to both the treatment arm and the observation arm, molecular assessment of the immune dysfunction in this high-risk patient group is assured. Minimal residual disease (MRD) levels will be examined by quantitative highly sensitive flow cytometry (MRD flow) in the peripheral blood and in the bone marrow at: The Department of Hematology, Rigshospitalet, Copenhagen University Hospital.

• MRD assessment: MRD will be quantified by eight-color flow cytometry with a sensitivity of at least 10⁻⁴ as previously validated against ASO-primer real-time quantitative IGH-PCR.³⁵ MRD assessments of peripheral blood are to be performed at screening (for baseline characterization of the individual CLL clone), at 3 and 6 months after treatment initiation/start of observation, thereafter once a year for 2 years.

In addition, an NGS capture-based assay for MRD detection based on recurrent mutations and IGHV sequence is under development. DNA is prepared from patient samples at time of MRD assessment by flow cytometry. After full enrollment, these DNA samples will be analyzed by the NGS assay to allow for direct comparison of MRD assessment by the two methods and to allow for assessment of subclonal development during and after treatment. Furthermore, BH3 profiling as

developed in collaboration with Assoc. [name], Dana Farber Cancer Institute, will be employed for assessment of sensitivity to various targeted therapies of viably frozen primary CLL cells from enrolled patients at baseline. The results of BH3 profiling will be correlated with long term outcome for the patients.

5.4 PROCESS FOR DECISION ON THE OPTIONAL EXPANSION TO PHASE 3

When the phase 2 part of the study is fully enrolled, the following assessments will form the basis for the decision on whether to expand the study to the optional phase 3 part with 212 patients in total:

- Non-inferiority for the phase 2 part as stated above should be met
- Immunophenotype analyses as outlined above have been reviewed
- Trend for benefit for patients in the treatment arm should be assessed
- DSMB do not find contraindications or safety reasons against expansion to phase 3
- Assessment by Abbvie, Acerta and the two study groups have been reviewed

The final decision to expand the study to the phase 3 part will be made by the sponsor, taking into account the input from the above-mentioned analyses and assessments.

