3.5 RATIONALE FOR STUDY DESIGN AND DOSING REGIMEN

Preclinical data supports the combination of BTK inhibitors and the bcl-2 inhibitor venetoclax. The combination of BTK inhibitors and venetoclax showed synergy in a diffuse large B cell lymphoma (DLBCL) cell line model ²⁸ and in primary CLL cells ³⁰ as well as in Mantle Cell Lymphoma (MCL) cell lines. ³⁶ Early clinical trials are currently testing the combination of venetoclax and acalabrutinib for clinical use, with no unexpected toxicities reported so far for combination of BTK and bcl-2 inhibitors through scientific meetings, publications or internal reports from the marketing holders. ³⁷ Translational data for patients treated with BTK inhibitors ^{6,25,26} and venetoclax ²⁷ indicate that immune function can be at least partly restored on treatment with decreasing incidence of infections over time on treatment and improved immune parameters. These translational data thus

support the hypothesis that short duration (3 months) treatment with the combination of acalabrutinib and venetoclax will improve the immune function for patients with newly diagnosed CLL at high risk of infection and/or treatment within 2 years.

Based on our collaboration with PERSIMUNE.org for multidimensional data-capture, genetic and functional analyses of primary CLL patient samples from our biobank covering samples from +700 patients since 2002 and machine-learning modelling in collaboration with DTU compute, we have developed a novel algorithm for identification of CLL patients at increased risk of infection prior to any CLL specific treatment and/or early CLL treatment, CLL-TIM (see figure 3-2). This model extends on known prognostic markers in CLL as defined based on the CLL-IPI criteria. 38,39 We are thus able to identify a subgroup of newly diagnosed CLL patients without IWCLL treatment indication, 40 who are at high risk of infection and/or treatment by the CLL-TIM. More than 65% of these patients will have a severe infection or CLL treatment within two years.

Figure 3-2. Performance of the CLL-TIM predicting high risk CLL patients for infection and/or treatment at time of diagnosis.

Agius et al, EHA 2018, Abstract PS-1103 and manuscript in preparation

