5. STATISTICAL METHODS OF ANALYSIS

5.1 GENERAL CONSIDERATIONS

The study is designed as a phase 2 study with an optional subsequent extension to a phase 3 study that can be considered if the conditions detailed below are met. Patients enrolled in the

phase 2 study will be included in the optional phase 3 study if the decision is made to extend the study. As the primary outcome for phase 2 is prior to and different from the primary outcome in the optional phase 3 part, this should not affect the power for the phase 3 study. Randomization is between observation and pre-emptive treatment with acalabrutinib and venetoclax for 3 months. Based on the CLL-TIM algorithm, newly diagnosed CLL patients with high (>65%) risk of severe infection and/or treatment within 2 years from diagnosis can be identified. Approximately 20% of newly diagnosed CLL patients will fall into this high-risk group.

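### The immune and MRD data are said to bear on 6 versus 3 months of treatment, but only a 3-cycle course is given, so any evidence on length is indirect

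*Protocol*

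**What the plan says.** The same sentence stands in section 3.4.3.1 (Assessment of Immune Dysfunction) and section 5.3.5 (Biomarker Analyses). Read with MRD and subclonal results, it says, "immune phenotyping data may indicate optimal treatment length (6 months or 3 months".

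The rest of the design has one treatment length:

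- Section 3.9: "Duration of treatment with acalabrutinib and venetoclax is for 3 cycles of 28 days". The synopsis and sections 3.2.1 and 3.8 agree, and the venetoclax table in section 3.7.5 ends with cycle 3.
- Section 5.1: "Randomization is between observation and pre-emptive treatment with acalabrutinib and venetoclax for 3 months".
- Section 3.5: existing translational data "support the hypothesis that short duration (3 months) treatment with the combination of" the two drugs.

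Section 5.3.5 schedules blood MRD at screening and then "at 3 and 6 months after treatment initiation/start of observation, thereafter once a year for 2 years". The synopsis places the primary assessment "12 weeks after finishing treatment, (24 weeks after treatment initiation".

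Section 5.4 lists, among the bases for the decision to expand to phase 3, "Immunophenotype analyses as outlined above have been reviewed".

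One further trace of a longer course remains. Section 6 takes the treatment period for safety assessment as the first 6 cycles, where the parallel text in the synopsis says the first 3.

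**The concern.** The sentence names two specific lengths and says the data may point to the better one. A reader would expect some patients to receive each length, and none is scheduled for the longer one. The nearest thing to a comparison of 3 with 6 is the pair of blood MRD samples at those times, and the 6 there counts months since the start, not months on drug.

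If the sentence is taken at face value, a difference between the two samples could be read as an argument for or against a longer course, when in treated patients it reflects stopping both drugs plus the passage of time. The immunophenotype analyses are also one of the items reviewed before expansion, and section 5.4 refers back to them as outlined in the section that carries this sentence.

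**Working it through.** **Inputs.** Course length: 3 cycles of 28 days (section 3.9). Primary assessment: 24 weeks after start (synopsis, sections 2.1 and 5.3.3). Blood MRD: 3 and 6 months after start (sections 3.4.3.2 and 5.3.5). Arms: 25 treated and 25 observed (synopsis).

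**The protocol's own figure.** On drug: 3 × 28 = 84 days = 12 weeks. At 24 weeks: 24 × 7 = 168 days, and 168 − 84 = 84 days = 12 weeks off drug. This reproduces the synopsis, which equates 24 weeks from initiation with 12 weeks after finishing.

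**The MRD times in calendar months** (365.25 / 12 = 30.44 days per month):

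| Sample | Days from start | Weeks from start | Weeks after day 84 |
|---|---|---|---|
| 3 months | 91.3 | 13.0 | 1.0 |
| 6 months | 182.6 | 26.1 | 14.1 |

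So the first sample falls at, or about a week after, the end of treatment. The second falls 12 weeks off drug if 6 months means the 24-week visit, and about 14 weeks off if it means calendar months.

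**What a 6-month course would be.** Six cycles are 6 × 28 = 168 days = 24 weeks. Patients scheduled for this: 0 of 25 in the treatment arm, 0 of 50 overall. No arm, cohort, extension or re-treatment rule in the protocol provides it.

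**What can be estimated.** Write Y(d, t) for a marker at day t after a planned course of d days.

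- The arms give Y(0, t) and Y(84, t). Randomization supports Y(84, t) − Y(0, t) at any sampling time.
- Within the treated arm, the MRD pair gives approximately Y(84, 168) − Y(84, 84). That is the effect of withdrawal plus time. The observation arm helps with the time part.
- A comparison of lengths needs Y(168, t) for t beyond day 84, and no patient supplies it. Up to day 84 a 168-day course on the same doses would look the same as the 84-day course. After that it must be extrapolated.

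A larger sample would make the first two quantities more precise and would not supply the third.

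**Immune markers.** The 3- and 6-month times are explicit only for blood MRD. Section 5.3.5 describes the immune assessment as taking place at baseline, during and after treatment. The argument does not need exact immune time points, because any sampling scheme within a single 84-day regimen leaves the longer course unobserved.

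**The case against.** The strongest reply is that the sentence promises little. It says the data may indicate, not that they will show. Treatment length is not among the primary, secondary or exploratory objectives, and no endpoint, test, threshold or decision rule uses it. Residual MRD at the end of the course, markers still moving on drug or already level, and rebound after stopping could each suggest that a course was short or sufficient. This stands, and it limits the criticism. A hedge, however, covers uncertainty about a result. Here the sentence names two lengths, one of which is never given, and does not say that the evidence on it would be indirect.

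Three stronger readings are tempting and are not supported:

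- **That the protocol makes selection of treatment length a purpose of the biomarker program.** One hedged sentence, printed twice, does not do that, and the hypothesis in section 3.5 concerns 3 months only.
- **That the data carry no information at all on length.** This is true of a direct comparison. It is not true of indirect, hypothesis-generating evidence.
- **That the phase 3 decision will choose a length on this evidence.** Section 5.4 decides whether to expand. It asks only that the immunophenotype analyses have been reviewed, alongside non-inferiority, a trend for benefit, the DSMB's view and input from the companies and study groups. Nothing there links a marker change to treatment length.

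Nor does the 6-cycle wording in section 6 show that a longer course is planned. It describes a window for safety assessment and is not a dosing instruction.

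**Conclusion.** The point holds in a limited form. The design compares 0 with 84 days of treatment, and 6 months is given to no one. The trial therefore cannot directly compare the two lengths that the sentence names. The MRD pair contrasts the end of treatment with about 12 weeks off both drugs (about 14 on a calendar reading), which is at most hypothesis-generating about length.

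Severity is low. No primary analysis or stopping rule depends on the sentence. What is at stake is the claim that can be made from secondary and exploratory data, and a possible misreading at the expansion decision.

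The off-drug intervals assume that treatment is completed on schedule; early stopping lengthens them. The absence of a 6-month group rests on all dosing sections agreeing. The window in section 6 is the one inconsistent figure, and it does not create such a group. A separate analysis plan could not remove the problem, because no analysis recovers an exposure that is not given.

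**What to change.** 1. In sections 3.4.3.1 and 5.3.5, remove the claim that the data can indicate which of the two lengths is optimal. State instead what they can show against observation: the depth of immune and MRD change at the end of the course, and its persistence after stopping. Label any inference on treatment length as hypothesis-generating.
2. In section 5.4, make clear that the immunophenotype review cannot be read as a comparison of treatment lengths. The sentence need go no further; it should not settle the regimen of a later phase.
3. Reconcile the 6-month wording in sections 3.4.3.1 and 5.3.5, and the 6-cycle treatment period in section 6, with the 3 cycles in the synopsis and section 3.9. This review takes no view on which length is right. Section 6 deserves attention in its own right, since that window separates treatment-period from follow-up events for the DSMB.

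The cost is a few sentences of text. No patient, sample, visit or sample-size change is involved, and the sponsor gives up only a claim that the design cannot support directly.
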